9.1.4 Efficacy and Safety Analysis (Part B)

The analyses for Part B will mirror the analyses of Part A, without testing any hypothesis. The detailed statistical analyses will be described in the Statistical Analysis Plan.

9.1.5 Interim Analysis (Int)

During the study, two Int will be performed to assess safety, tolerability and biological activity of the treatment (including data from the collected disease biomarkers at each of them). These analyses will be reviewed by an independent DSMB. The first Int will be carried out once the

first 30 patients have completed the 24-week visit (Int-6m) and the second one once all patients have completed the 24-week visit (Int-6m, eight weeks after the fifth monthly immunization), or in October 2020, whichever occurs first. The double blinding of the study will be maintained throughout these two Int. Additional DSMB reviews may be made *ad hoc* in the event of safety issues.

The DSMB statistical analysis plan (SAP) will provide the technical details of the Int.

. To assure blinding, all Int will be performed by an IS, who is not involved in any other tasks in this study.

9.1.5.1 Data Safety Monitoring Board (DSMB)

In order to assess safety and critical efficacy endpoints during the conduct of the trial, an independent DSMB has been appointed. The DSMB is an independent group consisting of three physicians who are not investigators in the study or other IMP development studies who have collective experience in the conduct and safety monitoring of clinical studies as well as monitoring and evaluation of clinical study safety data in randomized clinical studies in early phase. In addition, an IS will be also part of the DSMB.

The membership of the DSMB and the responsibilities of the DSMB are defined in the DSMB Charter. The Charter, signed by all DSMB members, includes detailed information about DSMB members' responsibilities, timing and purpose of DSMB meetings and Safety/Efficacy endpoints reviews of DSMB meetings, with their final recommendations.

The aims of the DSMB are to safeguard the interest of trial participants, assess the safety and efficacy of the interventions during the trial, and monitor the overall conduct of the clinical trial. Thus, the DSMB will provide recommendations and advice to the Sponsor. The Sponsor has overall executive responsibility over the Study. Any recommendation and/or decision will be taken in the best interest of the participants of this study, in order to safeguard their welfare and safety, and in accordance with CGP (ICH E6) and the latest version of the Declaration of Helsinki.

Schedules meetings of the DSMB will be face-to-face or by teleconference. These meetings will be classified as organizational meeting (kick-off) or formal data evaluation meetings.

At least two formal data evaluation meetings will be scheduled at:

1. Once the first 30 patients have completed the 24-week visit (Visit 16)
2. Once all patients have completed the 24-week visit (Visit 16), or in October 2020, whichever occurs first.

All two formal data evaluation meetings will be closed sessions and will include the safety endpoints as well as the main efficacy endpoints. At the three meetings, the DSMB will review the blinded/unblinded safety and efficacy data.

For the formal data evaluation meetings the IS will produce listings and summaries tables, including, but not limited to:

- Recruitment figures and losses to follow-up (all meetings)
- Demography and ApoE genotyping (all meetings)
- Safety parameters (all meetings):

- Number of withdrawn patients, number of patients who discontinued from treatment and reasons for withdrawal and discontinuation, respectively
- SAEs and AEs
- Rate (%) AEs
- Expected serious adverse drug reactions like Amyloid Related Imaging Abnormalities
- Physical and neurological examination significant abnormal findings
- Concomitant medication
- Vital signs (blood pressure, heart rate, respiratory rate, body temperature) and body mass index (weight, height) values.
- Safety Brain MRI
- Key EKG parameters
- Analytical haematology, toxicology (reactive protein), biochemistry, coagulation, serology and urine test strip results (all data regardless if they are abnormal).
- Average maximal increment ($M\Delta$) of anti-A β 40 antibody signal (OD in ELISA) (all meetings)
- A β 40 & A β 42 in plasma (all meetings)
- RBANS total score (all meetings)
- Results of futility analysis and sample size re-estimation (all meetings)

After each formal data evaluation meetings, the DSMB will provide recommendations to the Sponsor mainly in the following areas:

- Suspension of recruitment pending further safety review, if data received suggest significant adverse effect of the investigational medicinal product.
- Stop the study due to efficacy concerns (futility)*:
 - If, given the data up to the meeting's cut-off date, the futility analysis, based on the primary efficacy analysis (confirmatory) of superiority (meaning that the average maximal increment [$M\Delta$] of specific anti-A β 40 antibody signal [OD in ELISA] for the treated group is >0 OD to that of placebo group), yields a conditional power of less than 20% the DSMB will recommend to stop the study. Details on the futility analysis will be given in the DSMB SAP.

**A safety and efficacy reviews will be taken into account in order to make a recommendation*

- Increase the sample size based:
 - If pooled SD for the average maximal increment ($M\Delta$) of anti-A β 40 antibody signal (OD in ELISA) is higher than the estimated 1.6 (according to the results of the Phase I study), the DSMB will recommend to the sponsor to increase the sample size according to the observed pooled SD, to ensure at least 80% power to detect a treatment superiority with margin of 1.778 in average maximal increment (as considered in the secondary efficacy analysis [satisfactory])

Despite the statistical stopping rules indicated above, these are not formal rules; the recommendation to stop rests on the wise judgment of the DSMB on the basis of the totality of evidence at their disposal, both within the trial and externally. However, the ultimate decision rests with the Sponsor.

Details of the formal data evaluation meetings are included in the DSMB SAP and DSMB Charter.

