9.1.2.2 Secondary Efficacy Analysis

The trial will be considered satisfactory if the difference of the average maximal increment ($M\Delta$) of anti-A β 40 antibody signal (OD in ELISA) in the treated group is > 1.778 OD than the average $M\Delta$ in the placebo group; the difference that was reached between both groups in the phase I clinical trial of ABvac40.

The secondary efficacy variables regarding assessment of disease biomarkers and cognition (see section 7.1) will be analyzed descriptively in the overall group and separately in the amyloid-PET negative (verum and placebo) and the amyloid-PET positive (verum and placebo) subjects pertaining to the ITT and PP populations

For the exploratory comparison of the secondary efficacy variables for the characterization of the immune response (section 7.1.2) between the verum and placebo group, the maximal increment ($M\Delta$) with regard to the pre-treatment visit (either V0 or V1) in each subject will be used as a summary measure for each of the following variables: i) the OD signal for plasma peptides and cytokines levels, or A β plasma levels as determined by LC-MS, ii) the relative number of cells subsets from peripheral blood mononuclear cells; and iii) the number of cytokine and antibody producing cells. Statistical comparison between groups of treatment will be done for the variable $M\Delta$ by means of ANCOVA models, using the $M\Delta$ as the dependent variable, baseline as covariate and the treatment group and amyloid positivity as fixed effects. In addition, the number and percentage of patients in each visit reaching a value greater or equal than the $M\Delta$ will be tabulated by groups for each variable.

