9.2 Determination of Sample Size

This trial is intended as a confirmatory assay for the primary safety and primary efficacy variables.

For the safety primary endpoint, the sample size may be calculated to ensure $\geq 95\%$ probability of detecting an adverse event that occurs with a rate of at least 5% within the ABvac40 treated dose cohort. Under these assumptions, using the Hanley's simple approximation [32], a minimum of 60 patients in the active dose arm will be needed (and 60 in the placebo group).

This sample size (60 patients in the active group and 60 in the placebo group), considering $\sim 40\%$ dropouts along the clinical trial, will imply that approximately 70 patients will complete the study. These 70 patients will have greater than 85% power to detect a treatment increment of 1.778 (the one found in ABvac40 Phase I trial) in maximum change from baseline in anti- $\text{A}\beta 40$ antibody signal (OD in ELISA without preadsorption) between the active group and placebo group, using a one-sided T test at a significance level of 0.025 (and considering standard deviations of 2.0 and 1.0 in the active and placebo groups, respectively). The study will not be powered to demonstrate efficacy in clinical or other biomarker outcomes.

Thus, the screening will be continued until 120 individuals diagnosed with a-MCI or vm-AD with amnestic syndrome of the hippocampal type had been recruited into the trial and have received at least one dose of the Verum or placebo, as correspond. A minimum of 70 subjects are expected to complete the study per protocol (35 in each treatment group).

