3.2 Determination of Sample Size

For the primary safety endpoint, the sample size was determined to ensure the probability of detecting an AE that occurs with a minimum rate of 5% within the ABvac40 treated dose cohort is greater than 95%. Using Hanley's [1] simple approximation, a minimum of 60 patients per treatment group is required, i.e., total study sample size of 120 patients.

The total sample size of 120 patients, when considering a dropout rate of 40% during the clinical trial, should result in approximately 70 patients completing the study. In assessing the primary efficacy endpoint of no difference in the mean maximum change from baseline in anti-A β 40 antibody signal (OD), a one-sided t-test with a significance level of 0.025 will be employed. Assuming a difference of 1.778 O.D. between the active group and placebo group means with associated standard deviations of 2.0 and 1.0, respectively, there is greater than 85% power to reject the null hypothesis of no difference in the mean maximum change from baseline in anti-A β 40 antibody signal between the treatment groups. It should be further noted that the study may be insufficiently powered to demonstrate efficacy in clinical or other biomarker outcomes.

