6.1.2 Sensitivity Analyses for Primary Outcome

No adjustments will be made for multiple testing of study parameters. Therefore, interpretation of p-values for these sensitivity analyses should be considered descriptive in nature.

The following analyses will be performed for the primary outcome:

1. The primary analyses will be repeated for the PP Analysis Set.
2. The primary analysis (t-test) will be repeated, using the mITT Analysis Set to test the hypothesis:
 - Null hypothesis: average $M\Delta$ anti- $A\beta$ 40 (ABvac40) - average $M\Delta$ anti- $A\beta$ 40 (placebo) ≤ 1.778
 - Alternative hypothesis: average $M\Delta$ anti- $A\beta$ 40 (ABvac40) - average $M\Delta$ anti- $A\beta$ 40 (placebo) > 1.778
3. The change in anti- $A\beta$ 40 antibody signal from baseline to each post-baseline efficacy visit will be analyzed using a Mixed-Model Repeated Measures (MMRM), using the mITT Analysis Set.

The MMRM will include change from baseline in anti- $A\beta$ 40 antibody signal as the dependent variable; treatment, protocol-specified visits, treatment-by-visit interaction, and amyloid positivity as the fixed effects; baseline anti- $A\beta$ 40 antibody signal and baseline age as covariates; and measures within-patient at each visit as a repeated measure. The variance-covariance matrix will be assumed to be unstructured. If the procedure does not converge then a compound symmetric variance-covariance matrix will be used instead.

The least squares (LS) mean change from baseline will be presented for each treatment group (ABvac40 and placebo) for each post-baseline scheduled visit, along with the LS mean treatment difference (ABvac40 – placebo), 95% CI for mean treatment difference and p-value for comparison of treatment groups.

The following is sample SAS® code for the MMRM:

```
proc mixed data=pp method=ml;
  class Patient Treatment Visit a_PET;
  model change = Baseline a_PET Treatment Visit age
    Treatment*Visit / s;
  repeated Visit / type=un subject=Patient r;
  lsmeans Treatment*Visit / pdiff cl;
run;
```

A plot of LS means over time will be presented by treatment group.

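### The sample-size re-estimation rule promises 80% power for superiority by a margin of 1.778 OD, which cannot be reached when 1.778 OD is also the only planning difference

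*Protocol*

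**What the plan says.** Under Protocol 9.1.5.1, if the pooled SD of the maximal increment is above 1.6 (a value attributed to Phase I), "the DSMB will recommend to the sponsor to increase the sample size according to the observed pooled SD". The stated purpose is "to ensure at least 80% power to detect a treatment superiority with margin of 1.778 in average maximal increment", and the sentence refers to the secondary analysis that decides whether the trial is satisfactory. Protocol 9.1.2.2 defines that criterion as a between-group difference above 1.778 OD, "the difference that was reached between both groups in the phase I clinical trial of ABvac40". SAP 6.1.2, item 2, makes it a formal test with a null of a difference of at most 1.778, and cautions that "interpretation of p-values for these sensitivity analyses should be considered descriptive in nature".

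The planning assumption is the same number. Protocol 9.2 claims more than 85% "power to detect a treatment increment of 1.778 (the one found in ABvac40 Phase I trial) in maximum change from baseline". SAP 3.2 has "Assuming a difference of 1.778 O.D. between the active group and placebo group means with associated standard deviations of 2.0 and 1.0, respectively". Both sections apply it to the primary test, whose null is no difference.

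The futility rule in the same part of 9.1.5.1 uses that zero null. It concerns superiority in the sense that the average increment "for the treated group is >0 OD to that of placebo group), yields a conditional power of less than 20" percent. The section then adds: "Despite the statistical stopping rules indicated above, these are not formal rules".

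**The concern.** A sample size for a margin test depends on the distance between the assumed true difference and the margin. Here the two are the same Phase I figure, so the distance is zero and the SD has nothing to act on. The rule names only the SD as the quantity to update. Read literally, the DSMB is asked to find a sample size that does not exist. If it instead powers 1.778 against zero, the calculation can be done, but the 1.6 trigger does not fit the size of the trial. In both cases the sponsor could receive a recommendation to enlarge the trial that does not deliver the promised power or was not needed.

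**Working it through.** **Inputs.** One-sided alpha 0.025, planning difference 1.778 OD and SDs 2.0 and 1.0 (Protocol 9.2, SAP 3.2). Trigger SD 1.6 (Protocol 9.1.5.1). 60 per arm enrolled and 35 per arm expected to complete (Protocol 9.2). 15 per arm stated as enough for 85% power (Protocol 2.6). Root-mean-square SD = √((2.0² + 1.0²)/2) = 1.58.

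**1. Reproduce the plan's figure (null of zero).** n per arm = 2(z₀.₉₇₅ + z₀.₈₅)²·SD²/D² = 2(1.960 + 1.036)² × 1.6² / 1.778² ≈ 14.5, so 15 per arm. This matches Protocol 2.6. The noncentral t calculation gives 83.6% at 15 per arm and needs 16 for 85%. At 35 per arm the power is 99.6%.

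**2. The margin test as written.** Noncentrality = (D − 1.778) / (SD·√(2/n)). With D = 1.778 the numerator is 0 for every n and SD, so power = alpha = 2.5%. Calculation gives 2.5% at 15, 35, 60, 1,000 and 100,000 per arm; simulation gives 2.50% at 35 per arm and 2.48% at 500. A two-sided 5% test leaves the same 2.5% in the upper tail, and a one-sided 5% test gives 5%. If the criterion means only that the point estimate exceeds 1.778, the chance is about 50% at any n.

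**3. What the margin test would need (SD 1.6, 80% power).** The normal approximation at 35 per arm gives D = 1.778 + (1.960 + 0.842) × 1.6 × √(2/35) = 2.85. The noncentral t gives 2.86 at 35 per arm and 2.60 at 60. Patients per arm by assumed true difference (noncentral t):

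| True difference (OD) | n per arm |
|---|---|
| 2.0 | 817 |
| 2.25 | 182 |
| 2.5 | 79 |
| 2.75 | 44 |
| 3.0 | 28 |

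**4. The other reading: detect 1.778 against zero with 80% power.** Noncentral t gives:

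| Pooled SD | n per arm |
|---|---|
| 1.6 | 14 |
| 2.0 | 21 |
| 2.61 | 35 |
| 2.7 | 38 |
| 3.0 | 46 |

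Power stays at or above 80% up to a pooled SD of 2.617 with 35 per arm and 3.448 with 60 per arm. At the 1.6 trigger, power with 35 per arm is 99.6%.

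**5. How often the trigger is crossed.** The planning SDs pool to 1.58, just under 1.6. With normal data and true SDs of exactly 2.0 and 1.0, the observed pooled SD exceeds 1.6 at 42.3% of looks with 15 per arm, 42.5% with 18 per arm (the first look had 36 patients) and 41.5% with 60 per arm. It exceeds 2.61 at about 0.006% of looks with 15 per arm.

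**The case against.** The documents use 1.778 as an expected difference only for the primary test; they never say it is the truth expected for the margin analysis. A Phase I benchmark combined with a larger expected effect is coherent. Phase I gave two or three injections, this trial gives five plus a booster, and the endpoint is a maximum over all post-baseline visits. Protocol 9.1.5 and 9.1.5.1 defer technical detail to a DSMB SAP and Charter that may state the larger difference, and the DSMB sees the observed average increment. The formal null of 1.778 appears in an SAP that postdates the first look and the October 2020 limit for the second. On the against-zero reading, crossing 1.6 could simply prompt a recalculation that returns no increase, so 42% of looks is not 42% unnecessary expansions; that figure also assumes normal data.

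Much of this stands as a limit. The expected effect may well exceed 1.778, and the unseen DSMB SAP may say so. But the protocol and SAP quantify no such effect, and the rule updates only the SD. The later date of the SAP test does not help, because a point-estimate reading gives about 50%. The recalculation reading is charitable: the text says that an increase will be recommended once the SD passes 1.6.

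The practical stakes are small. The 60 per arm comes from the safety target and planned recruitment ended in September 2019. The remark that the rules are not formal is worded for stopping rules; re-estimation is advisory because the DSMB only recommends.

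**Conclusion.** The point holds, at minor severity. On the margin reading, which the reference to the secondary criterion supports, the protocol promises 80% power where its own inputs give 2.5% at any sample size. Reaching 80% at SD 1.6 takes a true difference of about 2.86 OD with 35 per arm or 2.60 OD with 60 per arm. On the against-zero reading the target is attainable, but the trigger of 1.6 should be about 2.61 at 35 per arm or 3.44 at 60.

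This rests on one-sided alpha 0.025, equal arms, t-based power and the absence of any planning difference above 1.778 in the protocol and SAP. The primary comparison against zero keeps 99.6% power at 35 per arm and is not in question.

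**What to change.** In Protocol 9.1.5.1, restate the target as at least 80% power to detect 1.778 OD against a null of zero, the null already used by the futility rule there. Recommend an increase only when the observed pooled SD takes power below 80% at the number expected in the primary analysis: above about 2.61 for 35 per arm, or about 3.44 if close to 60 per arm are analysed. The second figure may be the more relevant one, since the SAP's mITT set needs only a baseline and one post-baseline sample.

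If the sponsor prefers to keep the link to the margin, state the assumed true difference above 1.778 and the sample size that follows from it, or withdraw the 80% figure. Carry the same wording into the DSMB SAP.

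The cost is one sentence in each document. Restating the target against zero adds no patients. Its downside is that it drops the link to the satisfactory criterion and leaves a trigger that will rarely fire if the planning SDs are right.

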9.2 Determination of Sample Size

This trial is intended as a confirmatory assay for the primary safety and primary efficacy variables.

For the safety primary endpoint, the sample size may be calculated to ensure $\geq 95\%$ probability of detecting an adverse event that occurs with a rate of at least 5% within the ABvac40 treated dose cohort. Under these assumptions, using the Hanley's simple approximation [32], a minimum of 60 patients in the active dose arm will be needed (and 60 in the placebo group).

This sample size (60 patients in the active group and 60 in the placebo group), considering $\sim 40\%$ dropouts along the clinical trial, will imply that approximately 70 patients will complete the study. These 70 patients will have greater than 85% power to detect a treatment increment of 1.778 (the one found in ABvac40 Phase I trial) in maximum change from baseline in anti- $\text{A}\beta 40$ antibody signal (OD in ELISA without preadsorption) between the active group and placebo group, using a one-sided T test at a significance level of 0.025 (and considering standard deviations of 2.0 and 1.0 in the active and placebo groups, respectively). The study will not be powered to demonstrate efficacy in clinical or other biomarker outcomes.

Thus, the screening will be continued until 120 individuals diagnosed with a-MCI or vm-AD with amnestic syndrome of the hippocampal type had been recruited into the trial and have received at least one dose of the Verum or placebo, as correspond. A minimum of 70 subjects are expected to complete the study per protocol (35 in each treatment group).

9.3 Level of Significance to Be Used

The statistical tests will be performed with a 2.5% significance level for the primary efficacy (immunogenicity) variable and 5% for the and will be one-sided for the primary variable of biological activity and two-sided for the secondary biological activity/efficacy variables. In addition to the tests, 95% CI will be reported.

9.4 Criteria for Termination of the Study

The Investigator or the Sponsor may terminate this study prematurely for any reasonable cause. The Independent Ethics Committee(s) (IECs) and Competent Authorities (CAs) should be informed promptly.

Conditions that may warrant termination include, but are not limited to:

- The discovery of an unexpected, significant, or unacceptable risk to the subjects enrolled in the study, or potential study subjects
- A decision on the part of the Sponsor to suspend or discontinue development of the IMP

- If after analyzing the study data from Part A (up to month 18 – V23), no clinical differences have been observed between the Placebo and the Verum group according to the following stopping rules, the sponsor could prematurely finalize the study. At least one of the following criteria must have been fulfilled:
 1. For PET negative population: If the lower bound of the 95% exact CI for the proportion of negative PET patients treated with vaccine is greater than the proportion in Placebo group after 12 months (V21).
 2. For PET positive population: If the lower bound of 95% exact CI for the proportion of Reduction of cerebral amyloid plaques of positive PET patients treated with vaccine is greater than the proportion in Placebo group after 12 month (V21).
 3. For PET positive population: If the lower bound of the 95% exact CI for the mean of decline in Clinical Dementia Rating-Sum of Boxes (CDR-SB) in the positive PET patients treated with vaccine is greater than the mean in Placebo group after 18 months (V23).

If the CAs obtains information that raises doubts about the safety or scientific validity of the clinical study, the CAs can suspend or prohibit the study. Before the CAs reaches its decision it shall, except where there is imminent risk, ask the Sponsor and/or the Investigator for their opinion, to be delivered within one week (Directive 2001/20/EC, Article 12, Section 1).

If the study is prematurely terminated or suspended for any reason, the Investigator/institution should promptly inform the study subjects and should assure appropriate therapy and follow-up for the subjects.

